## 15.5 Analysis of Missing Data

Detailed summaries of missing data including the number and percentage of scheduled assessments with at least one of the four PROs completed will be provided. For each PRO, the percentage of scheduled assessments with fully completed PROs will also be provided. Other missing data methods to examine sensitivity and robustness of study results for the primary and key secondary endpoints will be described in the SAP. To minimize missing data, subjects will receive reminder notifications to complete their scheduled assessment.

## 15.6 Interim Review

When 100 subjects have enrolled, an interim review will be conducted by an External Advisory Committee to determine whether the study should continue or stop. The Advisory Committee decision to continue to enroll or stop will be made in consideration of several factors including but not limited to: overall rate of enrollment, adequate representation of sub-populations, missing PRO data, and prevalence of constipation as well as estimates of PRO variability. The two-stage enrollment strategy will allow for enriching enrollment based on either under-enrolled sub-populations or on the observed variability of GI symptoms for demographics-related factors such as age-group (pediatric/adult), modulator use or pancreatic status. In addition to the interim review, the TDNCC will continuously monitor enrollment and provide the Advisory Committee quarterly reports of enrollment demographics.

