### 15.2 Demographic and Baseline Characteristics

The enrolled study population will be described with respect to baseline demographic and clinical characteristics such as age, gender, race, ethnicity, genotype, height, weight, pancreatic status, body mass index, and use of concomitant medications. Demographics of subjects comparing completers (those who completed all questionnaires at all assessments) to those that are not completers will also be included. To evaluate the representativeness of the enrolled study population, the demographics of enrolled subjects will be compared against the general CF population (from the CFF Patient registry).

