2.3 Definition of the Analysis Populations

Enrollment:

An enrolled participant was defined as a participant who had met all eligibility criteria, and fully completed (i.e. no question left unanswered) at least one of the ePRO questionnaires (PAC-SYM, PAGI-SYM, PAC-QOL, and disease-specific) at baseline.

Baseline:

Baseline refers to the enrollment visit of enrolled participants, at which informed consent was given, eligibility was met, and medical history was collected.

Follow-up weeks:

GALAXY Statistical Analysis Plan 12/16/2019 - CONFIDENTIAL

Follow-up occurred at week 1 (day 7, +1), week 2 (day 14, +1), and week 4, (day 28, +1). These were outside-of-clinic, i.e. participants are asked to complete the ePRO via their mobile devices. The questionnaires took approximately 10 minutes to complete. For participants \geq 2 years of age to $<$ 12 years of age, the parent/guardian completed the questionnaire. For participants \geq 12 years of age, the participant completed the questionnaire.

Protocol-defined constipation:

Per protocol, constipation is defined as $<$ 3 bowel movements in the past week and/or Bristol Stool type 1 or 2.

3. Overview of Planned Analyses

Unless otherwise noted, the endpoints of this study are mostly descriptive, with all continuous outcomes such as symptom severity and PRO scores evaluated using descriptive statistics such as mean, median, standard deviation, and 95% confidence intervals. Presence/absence of symptoms will be shown as percentages and corresponding 95% confidence intervals calculated using the Wilson method. Longitudinal models will be mixed-effect models with participant-specific random effect and compound symmetry covariance structure. Except where otherwise noted, all tests will be two-sided and statistical significance will be determined at the 0.05 level. No adjustment for multiple comparisons will be made.

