3.4 Secondary Endpoints

3.4.1 The feasibility of ePRO surveys conducted outside-the-clinic setting:

1. At each scheduled outside-the-clinic assessment, number (%) of participants with at least one PRO fully completed
2. For each PRO, number (%) of participants with fully completed questionnaires at each scheduled outside-the-clinic assessment and overall
3. Number (%) of completed PROs by age and site

The corresponding analyses are outlined in Appendix A, Section A.3.

3.4.2 Prevalence and variability of GI symptoms:

Evaluation of PRO scores overall and by sub-scale at scheduled assessments:

4. Mean PRO score for PAC-SYM, PAGI-SYM, and PAC-QOL
5. Within- and across-participant variability of PRO scores

Descriptive statistics will be used to visually summarize the total scores and domain scores over time, and by age group. Longitudinal summaries will be provided, using mixed-effect models with participant-specific random intercepts. The corresponding analyses are outlined in Appendix A, Section A.4.

Evaluation of the prevalence of protocol-defined constipation:

6. Number (%) of enrolled participants with any occurrence of protocol-defined constipation during 1 month of follow-up (the period prevalence)

Descriptive statistics will be used to summarize the protocol-defined constipation, as well as other information from the disease-specific questionnaire over time, and by age group. The corresponding analyses are outlined in Appendix A, Section A.5.

Evaluation of the frequency and severity of each GI symptom at scheduled assessments and overall:

7. Number (%) of participants with presence of GI symptom
8. Distribution of severity scores of GI symptom
9. Mean severity score of GI symptom
10. Mean severity score of GI symptom
11. Distribution of stool frequency and type by Bristol Stool Scale

12. Change in distribution of GI symptoms and stool frequency/type from baseline visit overall

Pre-specified GI symptoms of interest, i.e. particular questions from the ePROs, are identified. Descriptive statistics will then be used to summarize the distributions of these GI symptoms overall, by age group, and the change from baseline. The corresponding analyses are outlined in Appendix A, Section A.5.

Evaluation of PAC-SYM, PAGI-SYM, and PAC-QOL scores by protocol-defined constipation:

13. Mean total and domain scores (also mean difference and 95% confidence interval) comparing participants with and without protocol-defined constipation

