		Protocol-Defined Constipation at Baseline		All Enrolled Participants (N=n)	Fully Completed at Least One ePRO at all Follow-up Weeks (N=n)	CF Registry (N=n)
		Yes (N=n)	No (N=n)			
Genotype, n (%)	F508 Heterozygous F508 Homozygous Other/Unknown					
Mutation Class, n (%)	I-III IV-V Unknown					
Sweat Chloride at Diagnosis (mEq/L)	Mean (SD)					
Weight (kg)	Mean (SD)					
Height (cm)	Mean (SD)					
Pancreatic Sufficiency[1], n (%)	Insufficient Sufficient Unknown					
Modulator Use, n (%)	None Ivacaftor Ivacaftor/Lumacaftor Ivacaftor/Tezacaftor Ivacaftor/Tezacaftor/Elexacaftor					

[1] Pancreatic Insufficient is defined as PERT use and/or fecal elastase or other diagnostic test at baseline.
Note on missing demographic data

Exhibit 5.2.2 Summary of Period-Prevalence of Constipation with Disease-Specific Questionnaire Fully Completed at all Weeks

This table summarizes the period-prevalence of protocol-defined constipation, as well as other definitions of constipation. Only participants who fully completed the disease-specific questionnaire at baseline and all follow-up weeks were considered. Period prevalence is defined as occurrence of the symptom at any time from baseline to week 4.

	Age <18 Years (N = n)	Age ≥18 Years (N = n)	All Participants (N = n)
Protocol-Defined Constipation ^[1] :	% (95% CI)		
Self-Described Constipation ^[2]			
Constipation			
Alternating Constipation and Diarrhea			
Alternative Definition:			
Definition 1			
...			
Definition d			

[1] Protocol-defined constipation is defined as less than 3 bowel movements and/or Bristol Stool type 1 or 2 in the past week

[2] Self-described constipation is based on the second question on the disease-specific questionnaire

Note: See Appendix B for discussion regarding alternative definitions of constipation.

Exhibit 5.2.3 Summary of Period-Prevalence of Constipation with Disease-Specific Questionnaire Fully Completed at least once

Similar table as above with consideration of participants who fully completed the disease-specific questionnaire at least once.

Exhibit 5.3.1 Summary of GI Symptoms from PAC-SYM, PAGI-SYM, and PAC-QOL

This table summarizes the GI symptoms based on prespecified questions from PAC-SYM, PAGI-SYM, and PAC-QOL questionnaires. All questions were based on patient's experience in the last week.

	Baseline	Week 1	Week 2	Week 4	Overall [1]
Symptom 1					
N [2]					
Absent, n (%)					
Mild, n (%)					
Moderate, n (%)					
Severe, n (%)					
Very Severe, n (%)					

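### If second-stage enrolment is enriched, the unweighted all-participants period prevalence of constipation shifts with the sample mix, and the SAP has no standardised figure to set beside it

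*Protocol*

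**What the plan says.** Protocol 15.6 sets up two stages: "When 100 subjects have enrolled, an interim review will be conducted by an External Advisory Committee". After that review, "The two-stage enrollment strategy will allow for enriching enrollment based on either under-enrolled sub-populations or on the observed variability of GI symptoms", and the sentence continues "for demographics-related factors such as age-group (pediatric/adult), modulator use or pancreatic status". With a ceiling of 400, the second stage is up to 300 subjects.

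The period prevalence of constipation is a secondary endpoint, and Protocol 15.4 names it as the one the sample size rests on. SAP 3.4.2 keeps it as a plain number and percentage. SAP Section 3 gives the interval: "Presence/absence of symptoms will be shown as percentages and corresponding 95% confidence intervals calculated using the Wilson method". Of Exhibit 5.2.2 the SAP says: "This table summarizes the period-prevalence of protocol-defined constipation, as well as other definitions of constipation", in columns for under 18, 18 and over, and all participants. It restricts the table further: "Only participants who fully completed the disease-specific questionnaire at baseline and all follow-up weeks were considered". Exhibit 5.2.3 repeats it for anyone with at least one complete disease-specific questionnaire.

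On representativeness, Protocol 15.2 says "the demographics of enrolled subjects will be compared against the general CF population", and SAP Exhibit 2.1 carries a registry column. Protocol 15.1.1 says stratification by age group, genotype, pancreatic status and DIGEST site will be considered for some endpoints; modulator use is not on that list. The SAP does not mention enrichment or enrolment stage, and neither document specifies weighting or standardisation.

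**The concern.** The first secondary objective in Protocol 3.2 concerns patients with CF, not the particular sample recruited. Once recruitment deliberately favours a stratum, a simple proportion over all participants estimates prevalence at the achieved mix. Its Wilson interval reflects sampling error only, so it can look precise while being centred away from the value at the population mix.

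The registry comparison would reveal an imbalance without correcting the estimate. The age columns protect a reader if enrichment was on age. They do not help if it was on modulator use or pancreatic status, because the SAP gives no period prevalence by either factor. Exhibit 5.2.1 cross-tabulates them only against constipation at baseline, so a reader could not re-weight the published figures.

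**Working it through.** **Plan's own figure.** Inputs from Protocol 15.7: prevalence 25%, half-width 4.5 points, 12% missing.

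- n = 1.96² × 0.25 × 0.75 / 0.045² = 355.7, so 356. Then 356 / 0.88 = 404.5, so 405, against approximately 400 stated. The plan's figure is reproduced.
- Evaluable subjects: 400 × 0.88 = 352. Half-width = 1.96 × √(0.1875 / 352) = 4.52 points. The Wilson interval is 20.8% to 29.8% (half-width 4.51).

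**Shift formula.** For two strata with prevalences p₁ and p₂, reference share W and achieved share w of stratum 1:

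shift = (w − W) × (p₁ − p₂)

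**Achieved share.** Take W = 40%, the planned paediatric share in Protocol 15.7 (160 of 400). For the other factors 40% is an assumption, since the documents give no population shares. Stage 1 (100 subjects) is at the reference mix, and a fraction q of stage 2 (300 subjects) comes from stratum 1.

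- q = 60%: w = (40 + 180) / 400 = 55%, a change of 15 points.
- q = 80%: w = (40 + 240) / 400 = 70%, a change of 30 points.
- q = 100%: w = (40 + 300) / 400 = 85%, a change of 45 points.

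**Coverage.** With b the shift and SE = √(p(1 − p) / 352) at the pooled prevalence p, coverage of the reference-mix value is Φ(1.96 − b/SE) − Φ(−1.96 − b/SE).

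**Standardised half-width.** 1.96 × √[W² p₁(1 − p₁)/(352w) + (1 − W)² p₂(1 − p₂)/(352(1 − w))].

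| Strata (p₁ / p₂) | q | Unweighted | At reference mix | Shift | Coverage | Half-width, unweighted | Half-width, standardised |
|---|---|---|---|---|---|---|---|
| Age, 30% / 32% (Protocol 15.7, one study) | 60% | 30.9% | 31.2% | −0.3 | 94.8% | 4.8 | 5.1 |
| same | 80% | 30.6% | 31.2% | −0.6 | 94.3% | 4.8 | 5.8 |
| same | 100% | 30.3% | 31.2% | −0.9 | 93.4% | 4.8 | 7.8 |
| Assumed 10-point difference, 31% / 21% | 60% | 26.5% | 25.0% | +1.5 | 90% | 4.6 | 4.6 |
| same | 80% | 28.0% | 25.0% | +3.0 | 76% | 4.7 | 5.2 |
| same | 100% | 29.5% | 25.0% | +4.5 | 54% | 4.8 | 6.9 |
| Assumed 20-point difference, 37% / 17% | 60% | 28.0% | 25.0% | +3.0 | 76% | 4.7 | 4.4 |
| same | 80% | 31.0% | 25.0% | +6.0 | 32% | 4.8 | 4.9 |
| same | 100% | 34.0% | 25.0% | +9.0 | 5% | 5.0 | 6.5 |

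Worked line, 20-point difference at q = 60%: shift = 0.15 × 20 = 3.0 points. SE = √(0.28 × 0.72 / 352) = 2.39 points and b/SE = 1.25, so coverage = Φ(0.71) − Φ(−3.21) = 76%.

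The shift reverses sign if the enriched stratum has the lower prevalence. It need not exceed the 4.5-point half-width to damage coverage: 1.5 points already costs about 5 percentage points.

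**The case against.** The strongest reply has four parts.

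- **Enrichment is permitted, not required.** Nothing in the documents shows that it happened. This stands, and it makes the point conditional.
- **Enrichment might help.** One of the two triggers is a shortfall in a sub-population, and Protocol 15.7 names representativeness as a design criterion. Used that way, it could move the sample closer to the CF population. This also stands. Whether it did so can be judged only by comparing the crude figure with a standardised one.
- **Enrichment works on strata.** Someone who stops at the reference to observed symptom variability might infer that symptomatic people would be selected. The rest of the sentence rules that out: the factors are demographic or clinical, so prevalence within each stratum is not distorted. Only the pooled figure is affected.
- **The documented effect is small.** For age, the only within-study contrast gives less than 1 point even if all of stage 2 were paediatric, and age-specific columns are already planned.

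A reader might set the 20% and 32% in Protocol 15.7 side by side as strata and conclude that the shift is larger (0.15 × 12 = 1.8 points at q = 60%). The documents do not support that. The 20% is an annual paediatric assessment under the ESPGHAN definition, and the 32% is for adults over 3 months in a different study.

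A reader might also infer that the headline figure would reflect the enrichment choice and not the CF population. That goes too far, because the pooled figure is a mix-weighted average of real stratum prevalences and depends on both.

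**Conclusion.** The gap is real but conditional. If enrichment is applied, the plan as written gives an unweighted pooled prevalence that can be off for the population mix, with no correction. For two of the three named factors it also gives no stratum figures from which a reader could make one.

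For age the effect is negligible on the documents' own like-for-like figures. For modulator use and pancreatic status its size is unknown; the 1.5 to 3.0 points and 90% to 76% coverage rest on the assumed stratum differences, a 40/60 reference mix, 60% of stage 2 from the smaller stratum and 352 evaluable subjects. Larger losses need more extreme recruitment or larger differences. The primary endpoint, ePRO completion, is not the subject of this point. This is an inexpensive improvement to a secondary estimate, not a flaw that undermines the study.

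**What to change.** 1. State in the SAP whether second-stage enrichment was applied and on which factor. The SAP already describes enrolment in the past tense, so this should be known.
2. If it was applied, add to Exhibits 5.2.2 and 5.2.3 the period prevalence by that factor.
3. In the same exhibits, beside the unweighted figure, add an all-participants estimate directly standardised to the registry distribution of that factor, with a matching stratified interval. Include age group in the standardisation where cross-classified registry counts can be obtained; Exhibit 2.1 as laid out gives each registry characteristic separately.
4. Describe the standardised figure as adjusted for sample mix on those factors only. It is not, without qualification, the prevalence in the CF population, because the eligibility criteria, the need to use the app and the questionnaire-completion restrictions remain.

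Cost: a few lines of analysis, plus a cross-tabulated registry extract if age is included. Precision usually falls somewhat. In the scenarios above the standardised half-width is 4.4 to 5.1 points at q = 60% and 4.9 to 5.8 at q = 80%, against about 4.5 planned. It reaches 6.5 to 7.8 only if stage 2 comes entirely from the smaller stratum. Where the higher-prevalence stratum is enriched the interval can even narrow slightly (4.7 to 4.4 in the 20-point case at q = 60%).

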## 15.7 Sample Size

[figure not shown]
Sample size estimates for this study are based on two criteria:

- a. To assess feasibility and ensure representativeness of the enrolled CF subjects
- b. To estimate prevalence of GI symptoms (specifically constipation)

Period prevalence is defined as the proportion of subjects with symptom over an interval of time. Estimates of constipation prevalence in CF patients varies in the literature. A recent 2017 publication (7) showed the period prevalence of constipation over 3 months was 31% (32% adults; 30% children). Another 2010 publication (3) estimated prevalence of constipation in CF patients age  $\leq$  18 years in the Netherlands at 20% (annual assessment) using the ESPGHAN definition. Note that an epidemiologic review of constipation prevalence in the general population (non-CF) in North America ranged from 1.9% to 27.2% with most estimates from 12%-19% (19). Therefore, 10% will serve as the lower bound estimate of constipation prevalence. The sample size estimate for CF patients in the GALAXY study is based on a prevalence of constipation over a 1 month period in the 20% - 30% range (25% average).

Sample size estimates are based on 95% confidence intervals (C.I.) half-widths (i.e., width of one arm of the 95% CI) for proportions. While constipation is one symptom of interest, it is difficult to specify an exact prevalence estimate over a 1 month period utilizing the study specific definition of constipation. In addition, the occurrence of other GI symptoms is also of interest and will occur at varying rates. Therefore, the figure below shows what the sample size (y-axis) is for varying half-width sizes (x-axis) when prevalence estimates range between 10% to 50% (maximum). Approximately 400 subjects are needed to estimate a prevalence of constipation of 25% with a 95% C.I. half-width of 4.5% (95% C.I. = 20.5%, 29.5%) and assuming a 12% missing data rate.

**Fig. 1: Sample Size for varying Prevalence Rates**  
**Prevalence of 10%, 20%, 25%, 30%, 50%**  
**by 95% C.I. Margin of Error (Half-Width)**

With 400 subjects, this study will allow estimation of variability (between and within subject) in 160 pediatric subjects and 240 adult subjects. A recent publication (20) reported PAC-SYM variability from 2884 adult patients with chronic constipation from six randomized clinical trials (scores range from 0 to 4 per subject). The study reported a baseline variance of 0.52. With 240 adult subjects and between-subject variance of 0.52, the 95% confidence interval for variance is 0.44, 0.63 (width = 0.19).

## 16 DATA COLLECTION, RETENTION AND CLINICAL MONITORING

### 16.1 Data Collection Instruments

The Investigator will prepare and maintain adequate and accurate source documents designed to record all observations and other pertinent data for each subject who signs informed consent.

Study personnel at each site will enter data from source documents corresponding to a subject's visit into the protocol-specific electronic CRF when the information corresponding to that visit is available. Subjects will not be identified by name in the study database or on any study documents to be collected by the Sponsor (or designee), but will be identified by a site number and subject number.

If a correction is required for a CRF, the time and date stamp tracks the person entering or updating CRF data and creates an electronic audit trail.

The Investigator is responsible for all information collected on subjects enrolled in this study. All data collected during the course of this study must be reviewed and verified for completeness and accuracy by the Investigator. At the completion of the study, a copy of the CRF data will be provided to the site to be retained at the Investigator's site.

## 16.2 Data Management Procedures

TDNCC utilizes Medidata Solutions, Inc. (Medidata) Rave for their study database. The Medidata Rave EDC system is designed to be US Code of Federal Regulations (CFR) 21 Part 11 compliant, with a robust audit trail system and electronic signature capabilities. Study personnel at each site will enter data from a subject's visit onto electronic CRF screens via a web browser. Study subjects will not be identified by name in the study database or on any data capture screens, but will be identified by a unique subject identification number. Only study personnel at the individual sites will be able to link the study ID to the subject's name. TDNCC also utilizes the Medidata Rave eCOA/ePRO system, a regulatory compliant system which allows subjects in a study using Medidata Rave EDC to complete and submit forms and data for patient-reported outcomes electronically on a mobile device to the Medidata Rave EDC System. Study personnel at each site will register study subjects using their unique subject identification number which generates an activation code unique to that subject. Study site personnel provide the subject with their activation code. The study subject downloads the Medidata Rave eCOA/ePRO app to their mobile device and uses their unique activation code to create their ePRO login and password.

The Biostatistics and Clinical Data Management group of the TDNCC will be responsible for data processing, in accordance with procedural documentation. Database lock will occur once quality assurance procedures have been completed. All procedures for the handling and analysis of data will be conducted using good computing practices for the handling and analysis of data for clinical trials.

## 16.3 Data Quality Control and Reporting

After data have been entered into the study database, data validation checks will be applied on a regular basis. Queries are entered, tracked, and resolved through the EDC system directly. The study database will be updated in accordance with the resolved queries. All changes to the study database will be documented in an audit trail.

